## SUMMARY

### **PrEP and dPEP: Doxycycline post-exposure prophylaxis for prevention of sexually transmitted infections among Kenyan women using HIV pre-exposure prophylaxis**

**Design:** Open-label 1:1 randomized clinical trial of doxycycline PEP to reduce bacterial STIs – *Neisseria gonorrhoeae*, *Chlamydia trachomatis*, and *T. pallidum* (syphilis) – among Kenyan women taking PrEP. We will also use quantitative questionnaires, focus group discussions, SMS, and in-depth interviews to study acceptability and changes in sexual behavior due to dPEP.

**Study Population:** 550 Kenyan women aged  $\geq 18$  and  $\leq 30$  years old taking PrEP randomized to dPEP and standard of care vs. standard of care alone

**Study Sites:** KEMRI RCTP – Lumumba clinic

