#### **Primary Study Objectives:**

1. Evaluate the effectiveness of doxycycline post-exposure prophylaxis (PEP) to reduce STI infections in HIV-uninfected Kenyan women taking HIV PrEP
2. Assess the safety, tolerability, and acceptability of dPEP
3. Assess adherence to dPEP
4. Investigate the impact of dPEP on tetracycline resistance in *N. gonorrhoeae* and *C. trachomatis*
5. Measure the cost of dPEP and estimate the cost per case averted, budget impact, and affordability.

**Approach:** We will conduct an open-label randomized trial of dPEP versus standard of care (STI screening and treatment and risk-reduction counseling without dPEP) among 550 women taking PrEP (1:1 allocation, 223 per arm). Women will be followed for 12 months, with quarterly STI testing, treatment, and adherence counseling. STI testing will be blinded. The trial will have  $>80\%$  power to detect a 50% reduction in curable STI incidence, overall and for *C. trachomatis* alone, the most common curable STI. We will use multidisciplinary science to measure a) tolerability and safety of dPEP (including effects on sexual behavior), b) acceptability, including challenges and motivators, of dPEP use, c) self-reported and objective measures of adherence to dPEP and PrEP, and d) occurrence of antimicrobial resistance in *N. gonorrhoeae* and *C. trachomatis* isolates using rigorous molecular methods. Finally, we will estimate cost per incident STI case and complications averted taking into account nonadherence and antimicrobial resistance.

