*Study visits:* Every 3 months, study visits will include STI screening, behavioral questionnaires, hair sample collection, and swab collection for archived samples. Women may return to the study clinic for interim visits for any reason and will undergo STI testing and treatment if STI symptoms are present. Participants with a new STI diagnosis will return for prompt treatment, provided on-site. Laboratory testing will be conducted by staff blinded to randomization assignment, and STIs will be reviewed by an Endpoint Adjudication Committee blinded to treatment arm. All participants diagnosed with an STI will either receive same day treatment or return to the research clinic for treatment, using WHO/Kenya standard therapies, avoiding doxycycline options, and a second visit two weeks following completion of STI treatment will be done for test of cure; this mitigates potential risk to participants and the community if resistance is selected.

*Study population:* This study will enroll approximately 550 Kenyan women aged  $\geq 18$  and  $\leq 30$  years old taking PrEP. PrEP use is an eligibility criterion for enrollment because we hypothesize that women engaging in PrEP are a priority population for prevention of curable STIs, given high incidence, interest in longitudinal preventative services, and willingness to take pills for prevention. Aligning with Kenya's national PrEP services, we propose an evaluation of the benefits, risks, and costs of dPEP among women, in the first trial of this intervention for this population. However, participants may opt to stop PrEP use at any time during the study without affecting their involvement in the study. Any HIV-uninfected participants who subsequently seroconvert will be managed clinically by the study site according to local practice (appropriate counseling, clinical evaluation and immediate linkage to clinical and psychosocial services). These participants will also be retained in the study unless they choose to discontinue study participation.

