### Statistical power and analysis

We propose a standard randomized superiority design, comparing dPEP to standard of care. The primary trial outcome will be the combined incidence of incident *C. trachomatis*, *N. gonorrhoeae*, and syphilis, compared between the randomization arms, to mirror the IPERGAY approach; analyses will also test each pathogen alone. We have been conservative in planning: first, we have planned for an STI incidence of 22% per year in the standard of care arm, which is less than the *C. trachomatis* incidence seen in our recent studies (**Table 3**) and second, we will calculate based on time to first incident STI alone, although we anticipate that some women will have repeat STIs contributing additional events and additional statistical power. We have planned for a 50% effect, comparable to the IPERGAY results and sufficiently great for public health benefit, but we anticipate that the *C. trachomatis* effect could be >50%, given universal susceptibility to doxycycline and

IPERGAY findings. With 80% power, 10% loss-to-follow-up, incidence of 22% vs. 11% (n=44 vs. 22 cases), and a two-sided alpha of 0.05, a sample size of n=550 is needed (n=275 per arm).

*Primary Analysis:*

We will analyze the composite endpoint of any of the three STIs as well as for *C. trachomatis* alone, and we will continue until there are sufficient *C. trachomatis* events (n=66) given the high incidence of this pathogen and its importance for reproductive morbidity (the consequence of which will be that the total number of events in the composite of *C. trachomatis*, *N. gonorrhoeae*, and syphilis will be greater than n=66). Analyses will be intention-to-treat, including women whether or not they continue dPEP (as well as whether or not they continue PrEP). STI incidence will be compared between arms using repeated measures analysis of proportions (e.g., generalized estimating equations [GEE]), given possibility of repeat infection within individuals. Per-protocol and adjusted analyses will be done as needed, controlling for potential confounders: demographics (e.g., age, education), sexual behavior (e.g., condom use, # partnerships), and beliefs (e.g., risk perception, dPEP/PrEP efficacy). SAS or R will be used.

*Secondary Analyses:*

Safety: Safety outcomes (i.e., AEs, tolerability, pregnancy, behavior) will be compared between arms using repeated measures analyses.

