## PROTOCOL SUMMARY

### PREP AND DPEP: DOXYCYCLINE POST-EXPOSURE PROPHYLAXIS FOR PREVENTION OF SEXUALLY TRANSMITTED INFECTIONS AMONG KENYAN WOMEN USING HIV PRE-EXPOSURE PROPHYLAXIS

**Design:** Open-label 1:1 randomized clinical trial of doxycycline PEP (dPEP) to reduce bacterial STIs – *Neisseria gonorrhoeae*, *Chlamydia trachomatis*, and *Treponema pallidum* (syphilis) – among Kenyan women taking PrEP. We will also use quantitative questionnaires, focus group discussions, SMS, and in-depth interviews to study acceptability, adherence, and changes in sexual behavior due to dPEP.

**Study Population:** 446 Kenyan women aged  $\geq 18$  and  $\leq 30$  years old taking PrEP randomized to dPEP and standard of care vs. standard of care alone

**Study Sites:** KEMRI RCTP – Lumumba clinic

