**Study population:** This study will enroll approximately 446 Kenyan women aged 18 and 30 years old taking PrEP. PrEP use is an eligibility criterion for enrollment because we hypothesize that women engaging in PrEP are a priority population for prevention of curable STIs, given high incidence, interest in longitudinal preventative services, and willingness to take pills for prevention. Aligning with Kenya's national PrEP services, we propose an evaluation of the benefits, risks, and costs of dPEP among women, in the first trial of this intervention for this population. However, participants may opt to stop PrEP use at any time during the study without affecting their involvement in the study. Any HIV-uninfected participants who subsequently seroconvert will be managed clinically by the study site according to local practice (appropriate counseling, clinical evaluation and immediate linkage to clinical and psychosocial services). These participants will also be retained in the study unless they choose to discontinue study participation

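### The protocol's sample size of 550 (275 per arm) does not follow from its own inputs, which fit the SAP's 446 (223 per arm)

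*Protocol*

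**What the plan says.** The protocol gives its calculation under Statistical power and analysis. It has "planned for an STI incidence of 22% per year in the standard of care arm", a 50% reduction, and states that "we will calculate based on time to first incident STI alone". With 80% power and 10% loss to follow-up it concludes: "incidence of 22% vs. 11% (n=44 vs. 22 cases), and a two-sided alpha of 0.05, a sample size of n=550 is needed", or 275 per arm.

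The figure of 550 recurs in the protocol Summary ("550 Kenyan women aged") and in section 2.0 ("This study will enroll approximately 550 Kenyan women aged"). The Approach paragraph of the Summary, however, has the trial "among 550 women taking PrEP (1:1 allocation, 223 per arm".

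The SAP uses a different size throughout. Its Protocol Summary has "446 Kenyan women aged", and section 3.1 says "This study will enroll approximately 446 Kenyan women aged 18 and 30 years old taking PrEP". Section 3.3.1 uses 22% versus about 11%, 44 versus 22 cases, 10% loss, two-sided alpha 0.05 and 80% power, and arrives at 446 (223 per arm) from a target of 66 events. It names nQuery and time to first STI within one year, but no formula. Table 2 of the SAP is computed for 446. Section 3.3.2 allows the sample size to be re-estimated when enrolment is nearly complete.

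**The concern.** One set of inputs carries two sample sizes, 104 women apart, in the two governing documents, and the protocol summary contradicts itself within a sentence. The case counts and power printed beside 550 appear to belong to 446.

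A reader cannot tell whether 550 is an error, an unexplained margin, or a raised target whose inputs were never updated. The ethics committees, the DSMB and the eventual trial report all need one planned size with the power that belongs to it.

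**Working it through.** **Inputs** (protocol, Statistical power and analysis; SAP 3.3.1): two-sided alpha 0.05, 80% power, 1:1 allocation, 22% versus 11%, hazard ratio 0.5, 10% loss, 44 + 22 = 66 cases, 12 months of follow-up.

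**Step 1. Reproduce the SAP's figure.** Schoenfeld events = 4(1.960 + 0.842)²/(ln 0.5)² = 65.3, so 66 = 44 + 22. Evaluable women per arm = 66/(0.22 + 0.11) = 200. Allowing for loss, 200/0.9 = 222.2, so 223 per arm and 446 in total. Expected cases at 446: 223 × 0.9 × 0.22 = 44.2 and 223 × 0.9 × 0.11 = 22.1, with power 80.5%. The SAP's figures agree with one another.

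**Step 2. The case counts alone.** No power formula is needed: 44/0.22 = 200 and 22/0.11 = 200 evaluable per arm, hence 223 per arm after 10% loss.

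**Step 3. Try the protocol's 275 per arm.** Evaluable: 275 × 0.9 = 247.5. Cases: 247.5 × 0.22 = 54.5 and 247.5 × 0.11 = 27.2, in all 81.7. To keep 44 versus 22 cases from 275 per arm, one of these must hold:
- loss of 1 − 200/275 = 27.3%; or
- incidence of 44/247.5 = 17.8% versus 22/247.5 = 8.9%.

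Neither is stated.

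**Step 4. Read 22% and 11% as annual rates.** The 12-month risks are 1 − exp(−0.22) = 0.1975 and 1 − exp(−0.11) = 0.1042, sum 0.3016. Schoenfeld: 66/0.3016/0.9 = about 243 per arm. Freedman needs [(1 + 0.5)/(1 − 0.5)]² × (1.960 + 0.842)² = 70.6, so 71 events: 71/0.3016/0.9 = about 262 per arm. Both are below 275.

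**Step 5. Cases and power at each size, 10% loss, hazard ratio 0.5.**

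| N | Reading of 22% | Cases | Power, Schoenfeld | Power, Freedman |
|---|---|---|---|---|
| 446 | 12-month proportion | 44.2 + 22.1 = 66.2 | 80.5% | 77.4% |
| 446 | annual rate | 39.6 + 20.9 = 60.5 | 76.9% | 73.7% |
| 550 | 12-month proportion | 54.5 + 27.2 = 81.7 | 87.9% | 85.4% |
| 550 | annual rate | 48.9 + 25.8 = 74.7 | 85.0% | 82.1% |

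Only the first row gives 44 versus 22 cases.

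**Step 6. Two smaller slips in SAP Table 2.**
- *Events for a 65% reduction.* The column heading puts 80% power at 52 infections. At 446 women with 10% loss (200.7 evaluable per arm), the 15% row implies 200.7 × (0.15 + 0.0525) = about 41 infections, yet prints 87%. The 18% row implies 200.7 × (0.18 + 0.063) = about 49, yet prints 92%. Fewer infections than 52 cannot give more than 80% power for the same effect. At hazard ratio 0.35, 80% power needs 29 events (Schoenfeld) or 34 (Freedman), and 52 events give 97% or 93%.
- *The 33% row.* Half of 33% is 16.5%, but the table prints 15.5%. By Schoenfeld the printed 93% matches 16.5% (93.2%), while 15.5% gives 96.1%. By Freedman the two values are 91.3% and 94.5%.

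**The case against.** The strongest objection is that 446 is not the only answer. Neither document names a formula, and the protocol says per year. Depending on formula and reading, totals at 80% power run from 396 (two proportions, no continuity correction) to about 524 (annual rates, Freedman). A continuity-corrected two-proportion test on the converted risks gives about 279 per arm, close to 275. This stands as a caution about the power formula, but it does not rescue 550. That test is not the time-to-first-infection calculation both documents name, and its 251 evaluable women per arm would yield about 50 versus 26 cases. The printed counts fix 200 evaluable per arm at the printed incidences whichever formula is used.

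A second objection is that 550 may be deliberate: a re-estimate under SAP 3.3.2, or extra women to secure 66 *C. trachomatis* infections alone, which both documents require. Either is possible, but neither is stated. The protocol presents 550 as needed for the listed inputs, the incidence is still 22% versus 11%, and the SAP's revision table lists no sample-size change. Some front-matter pages are not available, so a reason could lie there.

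Third, Table 2 is a separate matter from the 550 and 446 conflict. That is fair, and its two slips are minor. No single formula tried reproduces both columns (the 50% column is closer to Schoenfeld, the 65% column follows Freedman), so the software method should be named before the figures are replaced.

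**Conclusion.** The point holds. The protocol's 550 (275 per arm) is inconsistent with the 44 versus 22 cases, 22% versus 11% and 10% loss it cites. Those figures give 446 (223 per arm), as the SAP says, and the protocol summary pairs one document's total with the other's per-arm size. The gap is 104 women. At 550 the stated incidences would bring about 82 cases and 88% power (Schoenfeld; 85% Freedman) if they are 12-month proportions, or about 75 cases and 85% (82% Freedman) if they are annual rates.

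The case-count argument treats 22% and 11% as proportions of women completing 12 months; the power figures depend on the formula named. By the plan's own 66-event calculation with 12-month proportions, the composite endpoint reaches 80% power at either size. That comfort is conditional at 446: it falls to 77% if the incidences are annual rates, and to 77% by Freedman even with proportions. At 550 every variant in the table exceeds 80%. The figures should be corrected; endpoint, alpha and analysis model are unaffected.

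**What to change.** State one total, per-arm size, case count and power in the protocol Summary, section 2.0 and power section, and in the SAP Protocol Summary, sections 3.1 and 3.3.1 and Table 2. Match them to the target actually in force, and say whether 22% is a 12-month proportion or an annual rate.

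- **If the target is 446:** replace 550 and 275 in the protocol with 446 and 223. The text 44 versus 22 cases with 80% power is right only if 22% and 11% are declared 12-month proportions and the 66-event formula is named. With annual rates, state about 40 versus 21 cases and 77% (Schoenfeld; 74% Freedman).
- **If the target is 550:** give the reason, put 275 for 223 in the protocol Summary, change the SAP's 446 and 223, and recompute Table 2. State about 54 versus 27 cases and 88% power (85% Freedman) for 12-month proportions, or about 49 versus 26 and 85% (82% Freedman) for annual rates.
- **If 550 came from a lower observed rate:** state that rate. Keeping 44 versus 22 cases requires 17.8% versus 8.9%.

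In Table 2, recompute the 52 with the nQuery method actually used and name that method, and change 15.5% to 16.5%.

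The cost is wording and figures in two documents, provided they are matched to the target already in force. The documents do not say which target that is.

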### **Endpoint adjudication**

All STI endpoints will be reviewed by a blinded, independent Endpoint Adjudication Committee, following CDC guidelines for the diagnosis of STIs. Incidence of individual STIs and tetracycline resistance will also be evaluated.

## 12.0 PARTICIPANTS

### **Institutional Review Board (IRB) Review**

The study protocol, site-specific informed consent forms, participant education and recruitment materials, and other requested documents—including any subsequent modifications—will be reviewed and approved by the UW IRB, KEMRI SERU, and PPB ECCT in accordance with their requirements; they will be responsible for oversight of research conducted at the study site. Subsequent to initial review and approval, the UW IRB will review the study at least annually.

### **Informed Consent**

Written informed consent will be obtained from all study participants prior to enrollment in any study-related activities. Participants will be offered copies of the informed consent forms. Forms will be translated into local languages and verified by performing an independent back-translation. Informed consent forms will be kept in a secure and locked location for a period of at least 3 years following completion of the trial, longer if required by local regulations or requirements of overseeing IRBs/ECs.

### **Study records**

Each study site will establish a standard operating procedure for confidentiality protection. Each site will ensure that study records including administrative documentation and regulatory documentation as well as documentation related to each participant enrolled in the study, including informed consent forms, locator forms, case report forms, notations of all contacts with the participant, and all other source documents are stored in a secure manner.

### **Confidentiality**

Every effort will be made to protect participant privacy and confidentiality to the extent possible. Personal identifying information will be retained at the Kisumu study site and not forwarded to the labs in Mombasa, San Francisco, or Seattle, or to the University of Washington team; instead, all information will be identified only by study ID number. The site will use their standard operating procedure for confidentiality protection that reflects the input of study staff and community representatives to identify potential confidentiality issues and strategies to address them.

All study-related information will be stored securely at the study sites. All participant information will be stored

in areas with limited access. Data collection, administrative forms, laboratory specimens, and other reports will be identified only by the study ID number to maintain participant confidentiality. All records that contain names or other personal identifiers, such as locator forms and informed consent forms, will be stored separately from study records identified by study ID number. All local databases will be secured with password-protected access systems. Forms, lists, logbooks, appointment books, and any other listings that link participant ID numbers to other identifying information will be stored in a separate, locked file in an area with limited access.

### **Risks/Benefits**

Participants may experience pain or discomfort during blood draws pelvic exams, and rectal and nasal swab collection. They may be embarrassed or worried about the STI and HIV testing conducted during the study. Participants may also have some anxiety or worry about providing a hair sample, though the technique is optimized to minimize visible hair removal. Study questionnaires asking information about sexual behavior or partners may also make the participant uncomfortable or embarrassed. All study staff are trained to provide professional care in both clinical sample collection and counseling and administering study questionnaires. Counseling will be available to participants who feel they would benefit based on their experiences in the study.

Weekly SMS will be received outside of the study clinic and thus study staff cannot guarantee that someone other than the participant will see the message. The SMS will be coded so that if another person sees the message, it will not indicate the nature of the question or reveal that it is part of a research study. The participant may respond to the message at anytime she feels comfortable to do so, i.e. it does not require an immediate response. Additionally, if ever she would like to stop receiving the weekly SMS, she may request this from the study staff and she will be removed from the list of participants receiving the SMS.

For women assigned to the dPEP group, there are known side effects, as listed in protocol section 5.0. Participants will be counseled on the side effects and ways to take the medication in order to minimize the impact of any side effects. Participants will be encouraged to come to the study clinic if they have any concerns about the medication or side effects they are experiencing.

Study staff will make every effort to protect participants' privacy and confidentiality. It is possible that participants' involvement in the study could become known to others, and that social harms may result (i.e., because participants could become known as participating in a trial involving sexually active women or persons using PrEP). For example, participants could be treated unfairly or discriminated against, or could have problems being accepted by their families and/or communities. It is possible that participants may have problems with their partner or experience intimate partner violence. Counseling and referrals will be available, if needed.

Participants may benefit from their study participation as they will be receiving free STI testing and treatment that is not readily available in public clinics. Prompt treatment of STIs, including asymptomatic STIs, is beneficial to women in order to reduce the risk of pelvic pain, infertility, or other problems with future pregnancies that can develop when STIs go untreated.

### **Reimbursement**

Participants will be provided reimbursement for their travel costs and compensation of time spent during study visits, in accordance with local guidelines and regulatory approvals.

Participants who complete SMS surveys will receive airtime after 6 months of survey completion. Participants who continue to attend their follow-up visits may receive tokens of appreciation, for example study related gifts such as t-shirts or bags.

### **COVID-19 safety measures**

The Coronavirus Disease 2019 (COVID-19) pandemic is rapidly evolving and participant safety will remain a top priority in all study procedures. Study staff will follow all relevant local, national and WHO guidelines for minimizing exposure risk to participants, including but not limited to safety training, wearing appropriate

personal protective equipment (PPE), and enforcing social distancing. Specific procedures will be documented in a standard operating procedures (SOP) and updated as needed, particularly as more information about best practices for reducing COVID-19 transmission becomes available. During the consenting process, participants will be advised of the potential COVID-19 transmission risks related to in-person study procedures and the site procedures in place to minimize this risk.

